### Attention/Calculation:

- |  |    |                          |
|--|----|--------------------------|
| 5. Please take away 7 from 100             | 93 |  |
| Now continue to take 7 away from what      | 86 |  |
| you have left over until I ask you to stop | 79 |  |
|  | 72 |  |
|  | 65 |  |
6. Please count backwards from 20 to 1
- |             |                          |
|-------------|--------------------------|
| No mistakes |  |
|-------------|--------------------------|

### Comprehension, Semantic and Recent Memory:

- |   |              |                          |
|---|--------------|--------------------------|
| 7. What do people usually use to cut paper?             | Scissors     |  |
| 8. What is the prickly green plant found in the desert? | Cactus       |  |
| 9. What is the name of the reigning monarch?            | Correct Name |  |
| 10. What is the opposite direction to east?             | West         |  |
| 11. What is the surname of the prime minister?          | Correct Name |  |

### Language/Repetition:

- |   |               |                          |
|---|---------------|--------------------------|
| 12. Please listen carefully and repeat this:
"Methodist episcopal" | Exactly right |  |
|---|---------------|--------------------------|

**Delayed Recall:**

13. Please repeat as many of the 10 words I asked you to remember earlier

- Cabin
- Pipe
- Elephant
- Chest
- Silk
- Theatre
- Watch
- Whip
- Pillow
- Giant

**Score 1 point for each correct answer.**

Score \_\_\_\_\_

Score out of 39 (range 0-39). Death is assigned -1.

See 

**Concentration (from MMSE)**  
equivalent)

Spell WORLD backwards (or language specific

Score out of 5

**Verbal Fluency**

Now you have 1 minute to name as many animals as you can think of. Ready? Start now!

Write down each word and score 1 mark for each animal named. Do not score repetitions.

Score 0, 1, 2, 3, 4, 5 etc. Death is assigned -1.

See 

This protocol is confidential and the property of the University of Nottingham. No part of it may be transmitted, reproduced, published, or used by other persons without prior written authorisation from the University of Nottingham

## Appendix H. Zung Depression Rating Scale (short)

With scores:	Seldom or never	Some of the time	Good part of time	Most of time
I feel downhearted and blue	1	2	3	4
I have trouble sleeping at night	1	2	3	4
Morning is when I feel best	4	3	2	1
I can eat as much as I used to	4	3	2	1
I get tired for no reason	1	2	3	4
I find it difficult to make decisions	1	2	3	4
I feel hopeful about the future	4	3	2	1
I feel that I am useful and needed	4	3	2	1
My life is somewhat empty	1	2	3	4
I still enjoy the things I used to do	4	3	2	1

Short Zung IDS Index =  $100 \times \text{Total} / 40$ . Depression => 70. Death is assigned 102.5.

See 

## Appendix I. Frailty score on baseline neuroimaging

Component items: previous infarct (cortical or subcortical), atrophy, white matter changes

None                      No items present

Mild-moderate        1-2 items present

Severe                    All items present

Score out of 2 (range 0-2). Death is assigned 3.

See 

## Appendix J. Small vessel disease score on baseline neuroimaging

Component items: white matter hyperintensities (graded), lacunes

None	No items present
Mild-moderate	Mild-moderate WMH and/or lacune(s)
Severe	Severe WMH and lacune(s)

Score out of 2 (range 0-2). Death is assigned 3.

See 

## Appendix K: Expected events not subject to expedited reporting

The following events are expected with administration of glyceryl trinitrate and are, therefore, not subject to expedited reporting:

- Headache
- Hypotension
- Allergic skin reactions
- General allergic reactions

All of the events above are listed in the GTN summary of product characteristics.

After stroke the following events are expected and therefore not subject to expedited reporting”

### **Cardiovascular**

Acute coronary syndrome (ACS)

Angina: stable

Angina: unstable (UA)

Angina: type undefined

Atrial fibrillation (AF) or atrial flutter

Bradycardia

Cardiac (mural) thrombus

Cardiac dysrhythmia

Cardiac failure

Carotid dissection

Carotid stenosis: carotid endarterectomy

Carotid stenosis: no carotid endarterectomy

Carotid stenosis: carotid stenting

Chest pain (NOT cardiac)

Collapse

Deep vein thrombosis (DVT)

Endocarditis

Heart failure

Hypertension

Hypotension

Left atrial myxoma

Left ventricular failure (LVF)

Myocardial Infarction: NSTEMI

Myocardial Infarction: STEMI

Myocardial Infarction: type undefined

Patent foramen ovale (PFO)

Pericardial bleed

Peripheral Arterial Disease (PAD) / ischaemic limb

Sudden Cardiac Death (SCD)  
Supra-ventricular Tachycardia  
Systemic embolism  
Tachycardia  
Vasovagal episode  
Vascular event (not otherwise specified)  
Ventricular tachycardia (VT)

### **Nervous System**

Agitation  
Alzheimer's disease (AD)  
Anxiety / apprehension  
Brain Tumour: primary  
Brain Tumour: secondary  
Cerebral oedema  
Cognitive decline  
Complication of initial stroke  
Cortical vein thrombosis  
Deafness / hearing loss  
Dementia: type undefined  
Depression  
Dizziness  
Dysarthria  
Dysphagia  
Dysphasia  
Extension of initial ischaemic stroke  
Extradural haematoma / bleed (EDH)  
Extraspinal bleed  
Functional / Mimic / Pseudo Stroke  
Haemorrhagic stroke - primary haemorrhage/bleed  
Haemorrhagic transformation of infarction (HTI): HT1 or HT2  
Haemorrhagic transformation of infarction (HTI): HT1  
Haemorrhagic transformation of infarction (HTI): HT2  
Haemorrhagic transformation of infarction (HTI): PH1 or PH2  
Haemorrhagic transformation of infarction (HTI): PH1  
Haemorrhagic transformation of infarction (HTI): PH2  
Haemorrhagic transformation of infarction (HTI): type undefined  
Hallucinations  
Headache  
Hydrocephalus  
Intracranial aneurysm  
Intraspinal bleed / haematoma

Intraspinal infarct  
Ischaemic stroke: no blood  
Ischaemic stroke with HTI: HT1 or HT2  
Ischaemic stroke with HTI: HT1  
Ischaemic stroke with HTI: HT2  
Ischaemic stroke with HTI: PH1 or PH2  
Ischaemic stroke with HTI: PH1  
Ischaemic stroke with HTI: PH2  
Migraine  
Nerve Entrapment  
Neurological deterioration  
Neurological Event: NOT stroke/TIA  
Stroke: type undefined  
Sedation  
Seizure / Convulsions  
Sensory loss  
Stroke type: type unknown  
Subarachnoid haemorrhage (SAH)  
Subdural haematoma / bleed (SDH)  
Transient Ischaemic Attack (TIA) - imaging negative  
Transient Ischaemic Attack (TIA) - imaging positive  
Transient Ischaemic Attack (TIA) - no imaging  
Vascular dementia (VaD)  
Vertigo  
Visual loss  
Weakness

## **Respiratory**

Acute respiratory failure: type 1  
Acute respiratory failure: type 2  
Acute respiratory failure: type undefined  
Asthma  
Bronchitis  
Bronchospasm  
Chest infection  
Chronic obstructive pulmonary disorder (COPD)  
Chronic obstructive pulmonary disorder (COPD): exacerbation  
Epistaxis  
Emphysema  
Haemoptysis  
Hypoxia  
Interstitial pneumonitis

Pleural effusion  
Pneumonia  
Pneumothorax  
Carcinoma: primary lung  
Pulmonary embolism (PE)  
Pulmonary fibrosis  
Pulmonary haemorrhage  
Respiratory tract infection, lower (LRTI)  
Respiratory tract infection, upper (URTI)  
Secondary lung cancer  
Shortness of breath

### **Gastro-Intestinal**

Abdominal pain  
Bowel ischaemia  
Carcinoma: bowel  
Cholecystitis  
Colitis  
Constipation  
Diarrhoea  
Diverticulitis  
Dysphagia  
Gall stones  
Gastroenteritis  
Gastrointestinal disturbance  
Gastrointestinal infarction  
Haemorrhoids: bleeding  
Haematemesis  
Heartburn  
Hepatitis  
Hernia  
Incontinence: faecal  
Liver/hepatic impairment/dysfunction  
Lower GI bleed  
Melaena  
Nausea  
Oesophagitis  
Oral ulceration  
Pancreatitis  
Peptic Ulcer  
Carcinoma: primary liver  
Rectal bleed

Liver metastasis  
Stomatitis  
Upper GI bleed  
Vomiting  
Weight loss

### **Genito-Urinary**

Carcinoma: bladder  
Glomerulonephritis  
Haematuria  
Incontinence: urinary  
Kidney stones  
Penile bleed  
Carcinoma: renal primary  
Prostate cancer  
Renal cyst  
Kidney/renal impairment/failure/disease: acute (ARF)  
Kidney/renal impairment/failure/disease: chronic (CKD)  
Kidney/renal impairment/failure/disease: undefined  
Sexual dysfunction  
Urinary retention  
Urinary tract infection (UTI)  
Vaginal bleed

### **Haematological**

Acquired haemophilia  
Agranulocytosis/granulocytopenia  
Anaemia: type undefined  
Anaemia: aplastic  
Anaemia: microcytic  
Anaemia: macrocytic  
Haemoglobin drop: asymptomatic  
Haemoglobin drop: dilutional  
Haemoglobin drop: unidentified  
Eosinophilia  
Hypersensitivity including oropharyngeal swelling, urticaria, angioedema etc.  
Leukopenia  
Lymphadenopathy  
Methaemoglobinaemia  
Neutropenia  
Pancytopenia  
Polycythaemia

Thrombocytopenia  
Thrombotic thrombocytopenic purpura (TTP)  
Vasculitis

### **Immunological**

Haematological  
Allergic reaction  
Anaphylactic reaction  
Hypersensitivity

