## **Known side effects of placebo patches**

There is the possibility of allergic reactions to the product or its components. Patients who have a known sensitivity or allergy to the product or its components should therefore not participate in the study.

**Reference Safety Information:** Section 4.8 Transiderm Nitro SmPC

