Important medical events that may not result in death, be life-threatening, or require hospitalisation may be considered a serious adverse event when, based upon appropriate medical judgment, they may jeopardize the patient or participant and may require medical or surgical intervention to prevent one of the outcomes listed in this definition

All adverse events will be assessed for seriousness, expectedness, and causality:

A distinction is drawn between serious and severe AEs. Severity is a measure of intensity whereas seriousness is defined using the criteria above. Hence, a severe AE need not necessarily be serious.

Serious adverse events are common in stroke; a full list of expected SAEs that are not subject to expedited reporting are given in Appendix K.

As the IMP is administered once and has a short half-life, serious adverse events occurring within the first 2 days will be assessed for seriousness, expectedness, and causality. In addition, fatal SAEs will be reported until day 90.

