## **SUSARs**

**A serious adverse event that is either sudden in its onset (anaphylaxis), unexpected in its severity and seriousness or not a known side effect of the IMP *and* related or suspected to be related to the IMP is classed as Suspected Unexpected Serious Adverse Reaction and requires expedited reporting as per the clinical trials regulations.**

**All serious adverse events that fall or are suspected to fall within these criteria shall be treated as a SUSAR until deemed otherwise.**

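### The protocol gives conflicting instructions on expedited reporting of serious events related to GTN: the SUSAR definition names anaphylaxis, while Appendix K lists it as expected and not expedited

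*Protocol*

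**What the plan says.** Four parts of the Protocol bear on this.

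- **SUSARs.** A serious event that is "either sudden in its onset (anaphylaxis), unexpected in its severity and seriousness or not a known side effect of the IMP", and that is also related or suspected of being related to the IMP, is a SUSAR and must be expedited. Events suspected of meeting the definition count as SUSARs unless later judged not to. The Chief Investigator assesses seriousness, expectedness and relatedness. SUSAR data go to the regulator, and a report to the ethics committee, within seven days.
- **Adverse events, Definitions.** The text says that "a full list of expected SAEs that are not subject to expedited reporting are given in Appendix K".
- **Appendix K.** It has two lists. The first opens "The following events are expected with administration of glyceryl trinitrate and are, therefore, not subject to expedited reporting" and has four entries, one of them "General allergic reactions"; all four are said to be in the SmPC. The second opens "After stroke the following events are expected and therefore not subject to expedited reporting" and runs by organ system. Its Immunological block includes "Anaphylactic reaction". Its Haematological block includes "Methaemoglobinaemia" and an entry for hypersensitivity with throat swelling or angioedema.
- **Known side effects of placebo patches.** The reference safety information is given here as "Section 4.8 Transiderm Nitro SmPC".

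Under Reporting of adverse events, all serious events go to the regulator and ethics committee in annual safety update reports, with the faster route reserved for SUSARs.

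**The concern.** A related serious anaphylaxis meets the SUSAR definition by name and appears by name on the list of events that are not expedited. Someone following either section faithfully would contradict the other.

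The cause is that the two sources answer different questions. The SUSAR definition asks, in part, whether an event is a known side effect of the drug. The after-stroke list records events that may occur in stroke patients anyway. Once an event is judged related to GTN, its background frequency after stroke does not show that it is a known effect of GTN.

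What is at stake is how soon the regulator and ethics committee learn of a serious drug reaction. Safety is a stated purpose of the trial. Some patients, those who lack capacity and have no relative or friend available, may be treated under a waiver of consent. By the Definitions section, adverse events in general are not collected beyond hypotension, hypertension, headache and infection, so serious-event reporting carries much of the safety information.

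**Working it through.** The plan gives no figure on this point. The check is a comparison of passages.

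**Step 1: does Appendix K operate as a rule?** Yes. The Definitions section points to it as the full list, and each of its two lists opens with an instruction that the events are not expedited. Neither opening, nor the pointer, makes an exception for events judged related to the IMP.

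**Step 2: apply both rules to serious events judged possibly, probably or definitely related to GTN.**

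| Event | SUSARs section | Appendix K | In Table 3 (Known Side Effects)? |
|---|---|---|---|
| Anaphylactic reaction | SUSAR, expedited; named in the definition | Not expedited (after-stroke list) | No |
| Angioedema-type hypersensitivity | SUSAR if sudden, unexpected in severity and seriousness, or not a known side effect | Not expedited (after-stroke list) | No |
| Methaemoglobinaemia | As the row above | Not expedited (after-stroke list) | No |
| General allergic reactions | As the row above | Not expedited (GTN list, said to be in the SmPC) | No |

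Table 3's skin and application-site entries are contact dermatitis and local erythema, pruritus, burning and irritation. It has no systemic allergic reaction.

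**Step 3: what depends on the SmPC?** Row 1 does not, because the SUSAR wording names anaphylaxis outright. In rows 2 to 4, the part of the test that asks about known side effects depends on what section 4.8 lists. The SmPC is not among the documents. Table 3 cites the SmPC and omits general allergic reactions, while Appendix K says that they are in it. The Protocol's two summaries of the same source therefore differ, and neither settles the matter.

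**Step 4: is there a rule of precedence?** No. The Chief Investigator is told to assess expectedness but not whether to use section 4.8 or Appendix K.

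**Step 5: what does the choice change?** If the event is a SUSAR, the regulator and ethics committee are told within 7 days. If it is treated as expected under Appendix K, the stated route is the annual report, so the delay could be up to 12 months at the extreme. Two things do not change: the Chief Investigator is told within 24 hours, and the DMC receives safety reports every six months or more often on request.

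**The case against.** The strongest reply is that the SUSARs section already protects the anaphylaxis case. Its test is a list of alternatives, and sudden onset is one that does not turn on expectedness. Calling a related anaphylaxis expected would not take it out of that limb, and the presumption favours expediting. This stands in part. It lowers the chance that a report would be delayed. But the presumption lasts only until someone judges otherwise, and Appendix K offers a written ground for doing so. The reply is weaker for methaemoglobinaemia, which may depend on the known-side-effect limb.

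A second reply is that the after-stroke list is meant only for background illness. That is a reasonable reading, and the fix adopts it. The text does not say so. It is silent on related events, so it would also go too far to say that the Protocol expressly exempts these events whatever their cause.

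Three stronger readings are tempting and are not supported:

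- That a site could use Appendix K to downgrade an event. Every serious event goes to the Chief Investigator, who judges expectedness.
- That anaphylaxis or methaemoglobinaemia lies outside section 4.8. Absence from Table 3 does not show this, and Appendix K says that general allergic reactions are in the SmPC.
- That the length of Appendix K measures the problem. Most entries are plausible background illness, and some, such as headache, nausea and flushing, are in Table 3.

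**Conclusion.** The contradiction is real and should be corrected. For anaphylaxis it is direct and rests on the Protocol's wording alone. For angioedema-type hypersensitivity, methaemoglobinaemia and general allergic reactions, the Protocol offers two sources of expectedness and no rule for choosing between them; how far they conflict depends in part on what section 4.8 contains.

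The possible effect is late notification of the regulator and ethics committee. A reader might infer that a related anaphylaxis would go unreported or unseen. The documents do not support that, because the Chief Investigator and the DMC would still receive the information and the presumption favours expediting. No frequency can be given for these events, since the documents state none. The SAP's serious-event tables are laid out by timing, relationship and organ system and do not use expectedness, so no planned analysis is affected.

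**What to change.** Amend the Protocol so that the SUSARs section, the Definitions text under Adverse events, the reference safety information line and Appendix K agree:

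1. State that the after-stroke list applies only to serious events judged not related to the IMP.
2. State that, for serious events judged possibly, probably or definitely related (the Causality categories), expectedness is decided solely against the named reference safety information.
3. Check these Appendix K entries against that reference, and remove or justify each: general allergic reactions (GTN list); allergic reaction, anaphylactic reaction and hypersensitivity (Immunological); hypersensitivity (Musculoskeletal / Cutaneous); the angioedema-type entry and methaemoglobinaemia (Haematological). Editing the after-stroke list alone would leave the GTN-list entry in conflict.
4. State whether the anaphylaxis wording in the SUSARs section applies whatever the expectedness. Without this, step 2 could make anaphylaxis expected again if section 4.8 proves to cover it.

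The cost is a protocol amendment, a check against the SmPC and possibly some additional expedited reports. The SAP needs no change.

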### **Metabolic / Endocrine**

Acid base disturbance  
Dehydration  
Diabetes mellitus (Type II)  
Electrolyte disturbance  
Hyperglycaemia  
Hyperthyroidism  
Hyperuricaemia  
Hypoglycaemia  
Hypothyroidism

### **Musculoskeletal / Cutaneous**

Arthritis / arthralgia  
Bleed: gingival  
Bleed: skin  
Bruising, ecchymoses  
Bullous dermatitis  
Cellulitis  
Cramps  
Eczema  
Flushing  
Fractured bone  
Gout  
Hypersensitivity  
Intra-articular bleed, haemarthrosis  
Intramuscular bleed with compartment syndrome  
Intramuscular bleed without compartment syndrome  
Muscle twitching

**ABBREVIATIONS**

Abbreviation	Full Text
ACS	Acute Coronary Syndrome
ASU	Acute Stroke Unit
BLR	Binomial Logistic Regression
CI	Confidence Interval
CPHR	Cox Proportional Hazard Ratio
cSVD	Cerebral small vessel disease
CT	Computed Tomography
CTA	Computed Tomographic Angiography
COVID-19	Coronavirus
DBP	Diastolic Blood Pressure
DMC	Data Monitoring Committee
DNR	Do Not Resuscitate
DOAC	Direct Oral Anticoagulants
DSRS	Dysphagia Severity Rating Scale
ENOS-2	Efficacy of Nitric Oxide Trial 2
EQVAS	EuroQol-Visual Analogue Scale
EQ-5D-5L	EuroQoL- 5 Dimension- 5 Level quality of life questionnaire
FF	Fresh Frozen
GCS	Glasgow Comma Scale
GTN	Transdermal glyceryl trinitrate
HDU	High Dependency Unit
HT	Haemorrhagic Transformation
HSUV	Health Status Utility Value
ICH	Intracerebral Haemorrhage
IHD	Ischaemic Heart disease
IMP	Investigational Medicinal Product
IMPD	Investigational Medicinal Product Dossier
IS	Ischaemic Stroke
IV	Intra-venous
ITT	Intention to treat
ITU	Intensive Therapy Unit
LAD	Large Artery Disease
LVO	Large Vessel Occlusion
MEB	Major Extracranial Bleeding);
MHRA	Medicines and Healthcare products Regulatory Agency
MLR	Multiple Linear Regression
MMSE	Mini-Mental State Examination
MRI	Magnetic Resonance Imaging
mRS	modified Rankin Scale
NG	Nasogastric
NIH	National Institutes Health
NHS	National Health Service
NIHSS	National Institutes Health Stroke Scale
NO	Nitric oxide
NTG	Nitroglycerin
NUH	Nottingham University Hospitals NHS Trust
OLR	Ordinal Logistic Regression

PACS	Partial anterior circulation syndrome
PAD	Peripheral Arterial Disease
PEG	Percutaneous Endoscopic Gastrostomy
PICH	Primary intracerebral haemorrhage
POCS	Posterior Circulation Syndrome
PP	Per protocol
QOL	Quality Of Life
RTI	Respiratory Tract Infections
SAE	Serious Adverse Event
SAP	Statistical Analysis Plan
SAR	Serious Adverse Reaction
SAS	Statistical Analysis System
SBP	Systolic Blood Pressure
SC	Subcutaneous Fluids
SRU	Stroke Rehabilitation Unit
SVD	Small vessel disease
TACS	Total Anterior Circulation Syndrome
TGA	Transient Global Amnesia
TIA	Transient Ischaemic Attack
TICS-M	Telephone Interview for Cognitive Scale-Modified
TSC	Trial Steering Committee
UoN	University of Nottingham
UTI	Urinary Tract Unit
ZDS	Zung Depression Scale

## **SECTION 2. INTRODUCTION**

### **6 Background and rationale**

**Stroke:** Is common (life-time risk 1/5-6) and devastating (death 25%, dependency 40% at 1 year). Acute treatment is limited to alteplase, mechanical thrombectomy, aspirin, hemicraniectomy and stroke unit care. Anticoagulation is ineffective, neuroprotection unproven, and there is no widely-agreed treatment for intracerebral haemorrhage (ICH) although lowering blood pressure (BP) may be beneficial. Developing new interventions in hospitals has failed, in part, due to delayed treatment beyond the 'golden' hour after stroke. The management of physiological disequilibrium - BP, oxygen, glucose, cerebral oedema - remains unclear, and it is reasonable to hypothesise that their treatment, if warranted, should start rapidly after stroke onset.

**High BP:** Is common (80%) in patients with acute IS and ICH, and is associated independently with increased early recurrence and late death or dependency. Whether lowering BP improves outcome through reducing expansion and recurrence, or worsens it through reducing cerebral blood flow (due to dysfunctional autoregulation) remains unclear, in part because most trials started treatment several hours after onset. When assessing functional outcome, trial results have varied from a strong positive trend (INTERACT-2: SBP 14 mmHg lower with intensive treatment in ICH) through neutral effect (IMAGES: BP 4/3 mmHg lower with intravenous magnesium in mixed IS/ICH; CATIS: systolic BP 9 mmHg lower with intensive treatment in IS; ENCHANTED-BP SBP 5.5 mmHg lower with intensive BP-lowering in IS) to strong negative trend (BEST: oral propranolol or atenolol in mixed IS/ICH; INWEST: intravenous nimodipine in IS; SCAST: BP 5/2 mmHg lower with oral candesartan in mixed IS/ICH). Meta-analysis, and meta-regression of trial outcomes versus BP change, have not identified benefit.

**Nitric oxide (NO) and donors such as glyceryl trinitrate (GTN):** Are candidate treatments for acute stroke and multiple mechanisms exist by which they might be effective; taken together, these actions may 'buy time' for the brain, protect it and prime patients for arterial reperfusion therapies:

- NO/GTN lowers BP in acute/subacute stroke and so may 'move' patients down the epidemiological curve relating high BP and poor outcome. This mechanism may be of particular relevance in ICH.
- NO dilates cerebral arteries (e.g. middle cerebral) so could increase 'front door' cerebral blood flow (CBF) and peri-lesional perfusion, as seen in the GTN-3 pilot trial.
- NO dilates pial arteries (shown experimentally) so might increase CBF via the 'back-door'.
- NO donors are neuroprotective in preclinical stroke, especially if given early.
- Endogenous NO levels are low in acute stroke; hence, administration will supplement low [NO].
- GTN may 'prime' patients for rt-PA by lowering their BP so that more can be treated, and more rapidly after hospital arrival. RIGHT showed non-significant trends for these.
- GTN, through cerebral vasodilation, may increase access of alteplase to obstructing clot and therefore increase the effectiveness of thrombolysis, i.e., GTN might be additive to rt-PA.

Several NO donors are licensed in the UK and are used widely in patients with ischaemic heart disease, heart failure and severe hypertension; these include intravenous sodium nitroprusside and transdermal glyceryl trinitrate. One uncontrolled pilot study found that sodium nitroprusside lowered BP without altering cerebral perfusion (assessed using CT SPECT), and attenuated platelet function, in patients with recent ischaemic stroke. Four phase II and two phase III randomised controlled trials have assessed transdermal glyceryl trinitrate in patients with acute stroke (IS and ICH) (Table A).

